### Secondary Outcome Analyses

- Pearson correlation to examine relationships between anxiety levels and sub-dimensions of treatment adherence.
- Subgroup analyses by demographic factors (age, gender, education level).

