**6. OUTCOME MEASURES****Primary Outcomes:**

1. Anxiety level measured by Beck Anxiety Scale (BAS).
2. Treatment adherence measured by the Patient Compliance Scale for Type 2 Diabetes Mellitus Treatment.

Secondary Outcomes:

- Sub-dimension scores of the treatment adherence scale, including emotional factors, knowledge factors, lifestyle changes, and diet-related factors.

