## **8. STATISTICAL ANALYSIS**

- Statistical analyses will be conducted using SPSS version 25.0.
- Descriptive statistics: mean, standard deviation, frequency, and percentage.
- Independent t-tests will be used for between-group comparisons.
- Paired t-tests for within-group comparisons.
- Pearson correlation for relationships between anxiety and adherence.
- Significance level set at  $p<0.05$ .
- Cronbach's alpha will be used to assess the reliability of scales.

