### Primary Outcome Analyses

- Within-group analysis: Paired t-test comparing pre-test and post-test scores for anxiety and adherence.
- Between-group analysis: Independent t-test comparing post-test mean differences between intervention and control groups.

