## **SIGNIFICANCE LEVEL**

- All statistical tests will be two-tailed, with a significance threshold of  $p < 0.05$ .

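### The SAP specifies no between-arm comparison for the adherence sub-dimension scores, so as written it yields no treatment-effect estimate for any secondary outcome

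*Combined protocol and SAP*

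**What the plan says.** Protocol section 6 (Outcome Measures) gives two primary outcomes, anxiety and treatment adherence, and defines the secondary outcomes as "Sub-dimension scores of the treatment adherence scale, including emotional factors, knowledge factors, lifestyle changes, and diet-related factors".

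The SAP, under Secondary Outcome Analyses, has two items. The first is "Pearson correlation to examine relationships between anxiety levels and sub-dimensions of treatment adherence". The second is subgroup analysis by age, gender and education; it does not say which outcome is analysed or whether the arms are compared.

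The SAP's post-treatment comparison of arms is under Primary Outcome Analyses: "Between-group analysis: Independent t-test comparing post-test mean differences between intervention and control groups". The line before it names the outcomes that section deals with: "Within-group analysis: Paired t-test comparing pre-test and post-test scores for anxiety and adherence".

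Protocol section 8 (Statistical Analysis) says "Independent t-tests will be used for between-group comparisons". It names no outcome, and it lists Pearson correlation as a separate item.

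**The concern.** This is a randomized trial, and the estimate that randomization supports is a contrast between arms. The SAP is not silent on the sub-dimensions: it gives them a method, but one that answers a different question. The correlation between anxiety and, say, the diet sub-dimension describes how two measurements vary together across patients. It can be strong when the game has no effect, because more anxious patients may simply adhere less. It can be close to zero when the game works. The SAP also does not say at which time point, or in which arm or arms, the correlation is computed.

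An analyst who follows the SAP heading by heading would report correlations under the secondary outcomes and no treatment effect on them. If a comparison is then added after the data are seen, the choice of sub-dimensions, of post-test or change score, and of model is open.

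**Working it through.** **1. Which analysis is assigned to which outcome**

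| Place | Analysis | Outcome named | Post-treatment arm contrast |
|---|---|---|---|
| SAP, Primary Outcome Analyses | paired t-test | anxiety, adherence | no |
| SAP, Primary Outcome Analyses | independent t-test | none in the line itself; stands under the primary heading | yes |
| SAP, Secondary Outcome Analyses | Pearson correlation | anxiety with sub-dimensions | no |
| SAP, Secondary Outcome Analyses | demographic subgroups | none | not stated |
| Protocol section 8 | independent t-test | none | yes, generic |

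No row joins the sub-dimension scores to a comparison of arms. The SAP's Reporting section promises confidence intervals and effect sizes where appropriate, but does not tie them to the sub-dimensions.

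**2. The plan's own sample size figure (protocol section 4)**

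Inputs: effect size 0.768, power 85%, two-sided 0.05. The protocol does not name the test; I take 0.768 as a standardized difference between two independent means.

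- Normal approximation: n = 2(1.960 + 1.036)² / 0.768² = 30.4, so 31 per group.
- Noncentral t: 31.44, so 32 per group.

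The stated minimum of 32 per group reproduces. It does not bear on the gap itself, but it confirms the basis for the illustrations below.

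**3. Precision if the missing comparison were made (SD units)**

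Unadjusted half-width of the 95% CI = t(0.975, 2n − 2) × √(2/n).

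- n = 36 per arm: 1.994 × √(2/36) = 1.994 × 0.2357 = 0.470.
- n = 32 per arm: 1.999 × √(2/32) = 1.999 × 0.25 = 0.500.

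Adjusting for the pre-test score multiplies this by about √(1 − r²), where r is the pre-post correlation. The documents do not give r, so I assume a range. At 36 per arm:

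- r = 0.3: 0.470 × 0.954 = 0.448.
- r = 0.5: 0.470 × 0.866 = 0.407.
- r = 0.7: 0.470 × 0.714 = 0.336.

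**4. Multiplicity**

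Four sub-dimensions are named. Testing each at 0.05, and assuming independence, the chance of at least one false positive is 1 − 0.95⁴ = 0.185. With a Bonferroni level of 0.05/4 = 0.0125 and a true effect of 0.768 SD, the power of each test (noncentral t) is 75.4% at 36 per arm and 69.0% at 32, against 89.5% and 85.6% at the 0.05 level.

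**The case against.** The strongest reply is that protocol section 8 already provides independent t-tests for between-group comparisons, without limiting them to the primary outcomes, and lists correlation as an addition. Nothing in the SAP says that the correlation replaces the t-test. On that reading the sub-dimensions are covered and the SAP is merely terse. This stands in part: a reader might infer that the sponsor does not intend to compare the sub-dimensions between arms, and the documents do not establish that. It does not close the gap, because the generic line names no outcome, while the more specific SAP separates primary from secondary analyses and puts the comparison of arms under the primary heading only.

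A second reply is that no secondary question is left unanswered, because none is stated. That is correct. The objective and both hypotheses concern adherence and anxiety as such. A reader might infer that the trial fails a declared aim of finding which components of adherence improve, but section 6 lists the sub-dimensions as outcomes without an objective or hypothesis of their own. The gap is a listed outcome with no specified comparison of arms.

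Three smaller points also stand. Correlation is not the only item under the secondary heading, although the subgroup item does not supply the missing contrast. The half-widths describe the precision available, not harm done, and with listwise deletion (SAP, Data Management) fewer than 36 per arm may be analysed. Nor is there ground to predict that the correlations will be misreported as benefit: the SAP describes them plainly as relationships.

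**Conclusion.** The point holds as a gap in the SAP. Every secondary outcome lacks a specified between-arm estimate, and the one method that the SAP assigns to the sub-dimensions by name cannot supply it. The primary outcomes and both hypotheses are unaffected, so this is worth correcting but does not threaten the main conclusions.

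The data planned for collection would support the estimate: the scale is administered before and after the intervention in both arms. Precision would be moderate, with a half-width of roughly half an SD unadjusted and between about a third of an SD and just under half an SD adjusted. Those figures rest on 32 to 36 per arm for the unadjusted case, and on 36 per arm with an assumed pre-post correlation of 0.3 to 0.7 for the adjusted case. The multiplicity figure assumes exactly four independent sub-dimensions. Section 6 introduces its list with the word *including*, so there may be more, and scores from one scale are unlikely to be independent.

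**What to change.** Under Secondary Outcome Analyses in the SAP:

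- Add a between-arm comparison of the post-test score for every sub-dimension of the adherence scale, and list all of them by name.
- Adjust each for its own pre-test score (ANCOVA with arm and baseline), and preferably use the same model for the primary outcomes so that the two sets of results are comparable. Extending the existing independent t-test would also close the gap; ANCOVA is preferred for its precision.
- Report the mean difference between arms with its 95% CI.
- Either label these comparisons exploratory or state a multiplicity rule. The documents contain none at present.
- Keep the correlations between anxiety and the sub-dimensions as exploratory associations, state their time point and which arms they use, and say that they are not evidence of a treatment effect.

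The cost is a few lines of SAP text and one model per sub-dimension, with no new data. There are two further costs. Without a multiplicity rule the added tests carry the false-positive risk shown above, and with Bonferroni each loses power. Also, the rank-test fallback under Normality and Assumptions does not carry over to ANCOVA, so the SAP should say what is done if the model's assumptions fail.

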**4. SAMPLE SIZE**

The sample size was calculated using G\*Power 3.1.9.2 at a 95% confidence level, effect size 0.768, and power of 85%.

- Minimum required per group: 32 participants
- Total sample size: 72 participants (36 in each group)

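### Subgroup analyses by age, gender and education are planned without a method, outcome or cut-points, and no between-arm test named in the SAP can show whether the effect differs between subgroups

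*Combined protocol and SAP*

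**What the plan says.** The whole subgroup plan is one bullet in the SAP under Secondary Outcome Analyses: "Subgroup analyses by demographic factors (age, gender, education level"). It gives no test, outcome, age cut-point, education grouping or rule of interpretation, and does not call the analyses exploratory.

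The between-arm method elsewhere in the SAP (Primary Outcome Analyses) is: "Between-group analysis: Independent t-test comparing post-test mean differences between intervention and control groups". The section on normality and assumptions substitutes Mann-Whitney if assumptions fail. The Significance Level section applies one threshold to everything: "All statistical tests will be two-tailed, with a significance threshold of" p<0.05. Section 8 of the protocol adds nothing that bears on subgroups. Neither document contains a regression or ANOVA model with an arm-by-factor term.

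Protocol section 4 gives the size: "Total sample size: 72 participants (36 in each group").

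**The concern.** An independent t-test or Mann-Whitney test compares two arms. It does not compare one treatment effect with another. An analyst who follows the SAP and has to produce subgroup results has no named tool except a separate arm comparison in each stratum. The natural next step is to note which strata fall below 0.05. A significant result in women beside a non-significant one in men is not evidence that the effect differs. With small strata this pattern is common even when the effect is the same in everyone.

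At stake is the reading of the secondary results. A game that helps all patients equally could be described as suited to one sex, age band or education level, and nothing in the SAP guards against that.

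**Working it through.** **Inputs.** From protocol section 4: d = 0.768, power 85%, 36 per arm. From the SAP: two-sided alpha 0.05 and three factors. Assumed, because the documents are silent: each factor has two equal levels, so 36/2 = 18 per arm per stratum; the true effect is identical in both levels; the factors are independent of each other.

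**1. The plan's own figure.** The protocol states "Minimum required per group: 32 participants", calculated "at a 95% confidence level, effect size 0.768, and power of 85"%. For a two-sided independent t-test with the noncentral t distribution, noncentrality = d·√(n/2) and df = 2n − 2. At n = 32 and d = 0.768 power is 85.6%, and 32 is the smallest n that reaches 85%. The figure reproduces, so 0.768 can be read as a standardised mean difference. (The one-sided version gives 26 and does not reproduce it.) At the planned 36 per arm, power is 89.5%.

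**2. Power within one stratum.** The same formula with n = 18 gives p = 0.610 at d = 0.768, 0.308 at d = 0.5, 0.141 at d = 0.3 and 0.050 at d = 0.

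**3. Chance that exactly one of two strata is significant.** For equal strata this is 2p(1 − p):

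- d = 0.768: 2 × 0.610 × 0.390 = 0.476
- d = 0.5: 2 × 0.308 × 0.692 = 0.426
- d = 0.3: 2 × 0.141 × 0.859 = 0.242
- d = 0: 2 × 0.05 × 0.95 = 0.095

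For unequal strata it is p1(1 − p2) + p2(1 − p1). At d = 0.768, a split of 24 and 12 per arm (powers 0.740 and 0.436) gives 0.531, and a split of 27 and 9 (0.791 and 0.335) gives 0.596. The even split is therefore not an unfavourable choice at the design effect.

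**4. Three factors, one outcome.** Treating the factors' results as independent would give 1 − (1 − 0.476)³ = 0.856. That is too high, because the same 72 patients enter every split. Simulation with 36 per arm and three independent factors at about 50:50 gives at least one discordant factor in about 74% of trials at d = 0.768, 67% at d = 0.5 and 42% at d = 0.3.

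**5. The interaction test under the same conditions.** The false-positive rate is 5% per factor and outcome (simulated 0.050 at d = 0.768 and 0.053 at d = 0.5). Over three factors it is about 1 − 0.95³ = 0.143.

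| Same true effect in all patients | Separate tests, exactly one stratum significant | Interaction test, false positive |
|---|---|---|
| One factor, one outcome | 48% (d = 0.768), 43% (0.5), 24% (0.3), 9.5% (0) | 5% |
| Any of three factors, one outcome | 74% (d = 0.768), 67% (0.5), 42% (0.3) | about 14% |

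**6. Power of the interaction test.** With 18 per cell, the standard error of the difference between two stratum effects is √(4/18) = 0.471 SD. For a difference of 0.768 SD the ratio is 0.768/0.471 = 1.63, and power is 36%. For 0.384 SD it is 13%. These figures ignore any precision gained from the baseline score, because the documents give no pre-post correlation.

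**The case against.** The strongest objection is that the faulty procedure is not written down. The SAP does not say that each stratum will be tested separately or that strata will be compared by their p-values. That is inferred from the absence of any other between-arm test. This stands, and the rates above are conditional on it. What is documented is that the method is unspecified and that no named method answers the subgroup question.

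A reader might go further in three ways that the documents do not support:

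- *That the trial will probably report a false differential effect.* The calculation counts discordant p-values. Whether authors turn discordance into a claim is a further step to which neither document commits them. The hypotheses make no subgroup claim, and the Reporting section calls for confidence intervals and effect sizes where appropriate. Those would partly expose overlapping stratum effects, though they do not replace a test of the difference.
- *That the primary outcomes, starting with "Anxiety level measured by Beck Anxiety Scale (BAS"), will be subgrouped.* The bullet sits under the secondary analyses and names no outcome. Protocol section 4 also does not say which outcome the 0.768 belongs to.
- *That 18 per arm is a plan figure, or that 74% should be set against 5%.* The first assumes an even split. The second mixes three factors with one; the matching figure is about 14%.

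It can also be said that the better test has little power here, so the practical gain is restraint. That is true, but it argues for an exploratory label and does not make stratum-by-stratum testing valid.

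**Conclusion.** The point holds in conditional form. The SAP prespecifies three subgroup factors and supplies no method able to test for a differential effect. If the named tests are applied within strata, discordant results under a uniform effect are common: roughly one in two trials per factor and outcome at the design effect and one in four at d = 0.3, against one in twenty for an interaction test. The size depends on the true effect and on the assumed even two-level split. No rule in the SAP stops such discordance from being read as a subgroup difference. The primary between-arm comparison and the sample size are untouched, so this should be corrected but does not threaten the main result.

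**What to change.** Expand the subgroup bullet in the SAP's Secondary Outcome Analyses to state:

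- which outcomes are analysed by subgroup, and the levels or cut-points of each factor;
- that each factor is examined one at a time in a linear model of post-test score on arm, factor, arm-by-factor and baseline score. The SAP has no such model at present, so it must be written out;
- that the interaction estimate is reported with its 95% CI, and the stratum effects with their CIs;
- that a differential effect is claimed only on the interaction, never on which strata reach p<0.05;
- that these analyses are exploratory.

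The cost is a few lines of SAP text, including the new model. No extra participants or measurements are needed. The downside is insensitivity: about 36% power for a difference in effect as large as the design effect itself, so few subgroup claims could be made.

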### Reliability Testing

- Cronbach's alpha will be calculated for all scales to ensure internal consistency ( $>0.70$  acceptable).

## **NORMALITY AND ASSUMPTIONS**

- Normality will be assessed using Kurtosis and Skewness statistics.
- Homogeneity of variances will be checked using Levene's test.
- If assumptions are violated, non-parametric equivalents (Mann-Whitney U test, Wilcoxon Signed-Rank test) will be applied.

## **SIGNIFICANCE LEVEL**

- All statistical tests will be two-tailed, with a significance threshold of  $p < 0.05$ .

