### **Hypotheses**

- H1: Game-based diabetes education will significantly improve treatment adherence levels.
- H2: Game-based diabetes education will significantly reduce anxiety levels.

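### Two primary outcomes are each tested at 0.05 with no success or multiplicity rule; if either counts and both nulls are true, the false-claim chance is 7.0% to 9.75% against a nominal 5%

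*Combined protocol and SAP*

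**What the plan says.** Section 6 of the protocol lists two primary outcomes: "Anxiety level measured by Beck Anxiety Scale (BAS") and "Treatment adherence measured by the Patient Compliance Scale for Type 2 Diabetes Mellitus Treatment". The Hypotheses part of section 1 treats them one at a time: "H1: Game-based diabetes education will significantly improve treatment adherence levels" and "H2: Game-based diabetes education will significantly reduce anxiety levels". The Objective joins the two effects with the word *and*.

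On the threshold, protocol section 8 has "Significance level set at" p < 0.05 without naming a side. The SAP, under Significance Level, has "All statistical tests will be two-tailed, with a significance threshold of" p < 0.05.

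The SAP's Primary Outcome Analyses section holds two kinds of test. One is an independent t-test between the arms. The other is "Within-group analysis: Paired t-test comparing pre-test and post-test scores for anxiety and adherence".

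Section 4 sizes the trial with one effect size (0.768), 95% confidence and 85% power. This gives at least 32 per group, with 36 planned, and the outcome that 0.768 refers to is not named. No section ranks the two outcomes, splits alpha, names a multiplicity procedure, or says what counts as a successful trial. The SAP defines an intention-to-treat and a per-protocol set and names neither as primary.

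**The concern.** With two primary outcomes at the full 0.05 and no rule linking them, the plan can be read in three ways:

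- **Either outcome suffices.** The family-wise error exceeds 5%.
- **Both are required.** There is no inflation, but power for the joint claim differs from power for one test.
- **H1 and H2 are two separate claims.** Each carries its own 5%.

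The plan selects none of these, so the reading can be chosen after the results are known.

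The paired tests open a second route to a primary claim. The control arm also receives diabetes education for the same duration, so both arms could improve. A significant before-after change in the game arm could then be reported under the primary heading without any difference between the arms.

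**Working it through.** **Inputs from the documents.** Two primary outcomes (section 6); alpha 0.05 (section 8), two-sided for all tests (SAP, Significance Level); d = 0.768, power 85%, minimum 32 and planned 36 per group (section 4).

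**Assumed, not in the documents.** The correlation r between the two test statistics, signed so that benefit is positive on both, taken from 0 to 0.9; and d = 0.768 on both outcomes wherever joint or Holm power is given.

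**1. The plan's own sample size.** Two-sample t-test, noncentral t, with noncentrality d√(n/2) and 2n − 2 degrees of freedom.
- n = 32: 0.768 × √16 = 3.072, 62 df, two-sided 0.05: power 0.856.
- n = 31: power 0.845, just short of 85%.
- n = 36: 0.768 × √18 = 3.258, 70 df: power 0.895.
- One-sided 0.05 would need only 26 per group.

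So the stated 32 reproduces as one two-sided test at the full 0.05. It allows for neither an alpha split nor a joint requirement.

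**2. Either outcome counts, both nulls true.**
- Any false claim, r = 0: 1 − 0.95² = 0.0975.
- False benefit, r = 0: 1 − 0.975² = 0.0494.
- For r > 0, bivariate normal with cut-off 1.96:

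| r | Any false claim (nominal 5%) | False benefit (nominal 2.5%) |
|---|---|---|
| 0 | 9.75% | 4.9% |
| 0.5 | 9.1% | 4.5% |
| 0.7 | 8.3% | 4.2% |
| 0.9 | 7.0% | 3.5% |

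**3. Both must succeed.** At r = 0 joint power is the square of single-test power: 0.8950² = 0.801 at 36 and 0.8564² = 0.733 at 32. Simulated t-tests (200,000 trials per case) give, for r = 0.5, 0.7 and 0.9: 0.825, 0.838 and 0.863 at 36; 0.767, 0.784 and 0.816 at 32.

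**4. Holm.** Family-wise error at r = 0 is 1 − 0.975² = 0.0494, and it is at most 5% at any correlation. Single-test power at two-sided 0.025 is 0.831 at 36. At 36 per group:
- Both effects real, r = 0, per outcome: 0.831 + (0.895 − 0.831) × 0.831 = 0.884. Simulation gives 0.884, 0.875, 0.869 and 0.862 at r = 0, 0.5, 0.7 and 0.9.
- Only one effect real: 0.831 to 0.833.
- Both p values between 0.025 and 0.05, r = 0: (0.895 − 0.831)² = 0.004. By simulation this reaches about 0.016 at r = 0.9.

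**5. Paired tests, assumed example.** If both arms improve equally by 0.3 or 0.5 SD of the change score, a paired t-test in an arm of 36 is significant 42% or 83% of the time, with no between-arm effect.

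**The case against.** The strongest reply is that inflation belongs to only one of the three readings. The Objective's *and* leans towards requiring both outcomes, in which case testing each at 0.05 needs no adjustment. The separate hypotheses equally allow two distinct claims, each with a 5% error rate. Both readings are defensible, and a reader who infers that the plan as written has a 9.75% error rate goes further than the documents do. What remains is that a conjunction in an objective is not a decision rule, and no section adopts either reading.

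Independence also puts 9.75% at the high end of the range. The plan itself intends to correlate anxiety with adherence, so some correlation is plausible. The excess shrinks with correlation but is still there at 0.9.

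A reader might also infer that the trial is underpowered. The documents do not support that in general. For a single test, 36 per group gives 89.5%, and joint power at r = 0.9 is 86%. The shortfall depends on which rule is meant, and section 4 does not tie 0.768 to either outcome.

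Finally, the SAP specifies a between-group test beside the paired one, and its Reporting section promises exact p-values, with confidence intervals and effect sizes where appropriate. Readers could therefore make their own correction. That limits selective claiming but does not replace a rule set in advance. Nor do the documents say that a paired result would be claimed as primary; they only leave it possible.

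**Conclusion.** The gap is real and should be closed, but it does not invalidate the trial. If either outcome counts and both nulls are true, the chance of a false primary claim is 9.75% under independence and 9.1%, 8.3% and 7.0% at assumed correlations of 0.5, 0.7 and 0.9. The false-benefit share should be compared with 2.5%, not 5%; against 5% it would look harmless.

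If both must succeed, the error rate is sound. The 85% in section 4 then does not describe the trial's chance of success, which at 36 per group is 80% to 84% for r = 0 to 0.7 and 86% at r = 0.9, given d = 0.768 on both outcomes.

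These figures cover only the two between-group comparisons. The sub-dimension scores, correlations and subgroup analyses are already labelled secondary and are not counted.

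**What to change.** **Protocol section 8 and SAP, Significance Level.** State in both: *The two primary between-group comparisons (anxiety, adherence) are controlled at family-wise two-sided 0.05 by the Holm procedure; the smaller p is compared with 0.025 and, only if it passes, the larger with 0.05.* If the sponsor means the conjunction in the Objective, state instead: *The trial succeeds only if both between-group comparisons have p < 0.05.*

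**SAP, Primary Outcome Analyses.** Add: *Within-group paired tests are supportive and cannot carry a primary claim.*

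**SAP, opening section on analysis sets.** Add: *The primary comparisons use the Intention-to-Treat set.* That section admits participants with at least one session, whereas Handling Dropouts asks for a completed pre-test, so one definition is needed.

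**Protocol section 4.** Add: *32 per group and 85% power apply to a single outcome at unadjusted two-sided 0.05.* With it, give power for d = 0.768 at 36 per group under the chosen rule. Under Holm this is about 86% to 88% per outcome if both effects are real and 83% if only one is. Under the joint rule it is 80% to 86% for r = 0 to 0.9.

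**Cost.** Wording only, provided the rule is fixed before the between-group results are seen. Under Holm, a p between 0.025 and 0.05 whose partner is above 0.05 is no longer a primary claim. If both p values lie between 0.025 and 0.05, neither is; this happens in about 0.4% to 1.6% of trials at 36 per group with d = 0.768 on both. Under the joint rule, a clear result on one outcome alone is not a success. Should the sponsor want to keep 85%, Holm with one real effect needs 38 analysed per group (power 0.853), and the joint rule at r = 0 needs 40 (0.854).
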